#### 17.2 Power Analysis:

**Stigma Quantification:** The primary objective of this pilot study is to estimate the extent to which stigma towards PLWH (HIV stigma) and towards MSM (homophobia) contribute to the deterioration of healthcare quality relative to straight people without HIV. A total sample size of 160 standardized patient (SP) interactions would provide 80% power (alpha=0.05) to detect a minimum effect size of 0.18 standard deviation. This calculation is conservative in that it does not account for blocked randomization of the SP cases within practices, which will lend additional power to each comparison. Two-sided tests will be needed to detect differences across the four case scenarios in order to separately quantify HIV, sexual, and intersectional stigma, for which the same assumptions will provide the same amount of power to identify a minimum effect size of 0.17 standard deviation between any 2 pairwise comparisons of scenarios. As recruitment will take place at the clinic level, the number of participants that will be needed to be recruited to the study will depend on estimates of the average numbers of eligible providers that our team can reasonably expect to recruit at each clinic. Preliminary data suggest that clinics in our study region employ an average of 5 eligible providers, of whom we conservatively expect to recruit 70% or 3.5 per clinic. Each provider will receive 3 unannounced visits from a standardized patient, yielding a final estimated pool of 56 providers for this study.

**Preliminary intervention effects:** A secondary goal of the RCT is to estimate the preliminary effect of the intervention on quality of care index observed by SPs. Though this is only a secondary goal, we determine that it is plausible that the target enrollment of 20 clinics randomly allocated to treatment and control in a 1:1 manner could yield sufficient power to detect reasonably small effects on the primary outcome measure. That is, with an alpha level of 0.05 for a one-sided test, an intra-cluster coefficient of 0.07, and a baseline prevalence of standardized quality of care index (with mean of 0 and standard deviation of 1), a sample size of 160 SP clinic visits (8 visits per clinic on average) would provide 80% power to detect a reduction in EOC scores due to the intervention as small as 0.17 standard deviations.

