#### **ABBREVIATIONS/DEFINITIONS**

[figure not shown]
CAB	Community advisory board
EOC	Erosion of care
MSM	Men who have sex with men
GDCDC	Guangdong Center for STD Control and Prevention
PLWH	People living with HIV/AIDS
RCT	Randomized control trial
RERI	Relative excess risk due to interaction
ROR	Return of results
SMC	Safety monitoring committee
SP	Standardized patient
STD	Sexually transmitted disease

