## 11.0 Number of Participants

### 11.1 *Number of Participants to be Consented:*

To demonstrate the preliminary effectiveness of the intervention we recruited approximately 20 facilities within which an estimated 8 eligible providers work. For the baseline visits a total of 160 unannounced SP visits were made, or about 8 visits per clinic. Given the nature of patient intake procedures at outpatients facilities of the type that our SPs will visit, we were unable to control which of the consented providers in a given facility consented to SP visits. It is therefore possible that some consented providers in these clinics will never receive an unannounced SP visit, while others may receive multiple visits.

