## 12.0 Recruitment Methods

### 12.1 *Recruitment Process:*

Sampling of study facilities will take place across the 46 candidate STD practices across the Guangzhou metro area (Fig 2) and which meet our eligibility criteria of 1) having formal government accreditation as a medical center (a basic tenet of all public hospitals in China); and 2) possession of an accredited on-site laboratory with capacity to provide enzyme-linked immunosorbent assay testing for HIV, treponemal (e.g. Treponema pallidum particle agglutination) and non-treponemal tests (e.g. rapid plasma regain) for syphilis. Sampling will be conducted using a stratified approach to sample evenly across the 11 districts of Guangzhou city which includes urban and rural areas in order to maximize comparability between arms. Sampling will also consider travel distance between study facilities in order to minimize risk of contamination across arms following the intervention. Lastly, twice the number of facilities as needed for the final sample size will be screened and randomized in anticipation of the fact that a subset of facilities may refuse to take part in the study. Following randomization of sampled clinics, we will implement an additional randomization scheme to balance the distribution of the four SP scenarios (MSM only, HIV+ only, MSM and HIV+, and non-MSM HIV- man) and the 8 different SPs across the 20 study clinics. The scheme will also ensure that case scenarios and SP choice will be distributed over the clinic visit duration to balance the potential effects of these design features on our outcome measurement.

Recruitment took place in a staged manner, first at the facility level and then at the provider level. Following sampling and randomization of facilities to the treatment versus control condition (see Section 22.0 for justification of the randomization approach), facility directors of the chosen sites were contacted by [name], a co-investigator on this study and Director of the STD Clinical Quality Control Program at the GDCDC, as well as officials at a subsidiary organization at the Guangzhou City STD Control Center (GZCDC). STD control officials at the GZCDC report to their counterparts at the GDCDC for all matters pertaining to surveillance, disease control, and intervention work. Both [name] and his subordinates at the GZCDC maintain regular contact with administrators

PROTOCOL TITLE: Standardized Patients to Address Intersectional Stigma  
VERSION DATE: 07/23/2019

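### None of the three minimum detectable effects in section 17.2 (0.18, 0.17 and 0.17 SD) follows from its stated inputs; unadjusted they are about 0.39–0.51, 0.63 and 0.48 SD

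*Combined protocol and SAP*

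**What the plan says.** Section 17.2 (Power Analysis) gives three minimum detectable effects, all at 80% power.

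1. **Stigma, overall.** "160 standardized patient (SP) interactions would provide 80% power (alpha=0.05) to detect a minimum effect size of 0.18 standard deviation". Neither the contrast nor the sidedness is stated. The section adds: "This calculation is conservative in that it does not account for blocked randomization of the SP cases within practices".
2. **Stigma, pairwise.** With two-sided tests and otherwise unchanged assumptions and power, it claims "a minimum effect size of 0.17 standard deviation between any 2 pairwise comparisons of scenarios".
3. **Intervention.** With 20 clinics allocated 1:1, 8 visits per clinic on average, ICC 0.07, one-sided alpha 0.05 and an index with SD 1, 160 visits "would provide 80% power to detect a reduction in EOC scores due to the intervention as small as 0.17 standard deviations". This supports the statement that the design "could yield sufficient power to detect reasonably small effects on the primary outcome measure".

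Section 12.1 describes "an additional randomization scheme to balance the distribution of the four SP scenarios". Section 11.1 reports that the baseline round is complete: "For the baseline visits a total of 160 unannounced SP visits were made, or about 8 visits per clinic". The abbreviations list expands EOC as "Erosion of care", while the rest of the intervention paragraph refers to the quality of care index.

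**The concern.** An effect of 0.17 to 0.18 SD normally takes several hundred observations per group, and more when clinics are randomized. Here there are 80 visits per arm and about 40 per script.

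The figures also conflict with each other. A comparison of two scripts uses about half the visits, yet on unchanged assumptions it is given a smaller detectable effect (0.17) than the overall comparison (0.18). With power and assumptions held fixed, fewer visits cannot detect a smaller effect.

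Figures 1 and 2 concern what section 17.2 calls the primary objective. A reader who trusted them would take a null result as evidence against effects of about 0.2 SD, when the design would usually miss such effects. Section 15.1 expects a fully powered trial to follow, and reusing these figures there would understate the size it needs.

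**Working it through.** **Inputs.** From section 17.2: 160 visits, 80% power, alpha 0.05; for figure 3 also 20 clinics 1:1, 8 visits per clinic, ICC 0.07, one-sided, SD 1. Two assumptions are added: SD 1 for figures 1 and 2, and 40 visits per script, reading the balance in section 12.1 as equal counts.

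**Formula.** MDE = (z_alpha + z_0.80) × SE. The multiplier is 2.802 two-sided and 2.486 one-sided.

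**Attempts to reproduce the printed figures.**
- A one-sample test on all 160 visits gives 0.197 (one-sided) or 0.221 (two-sided).
- Cohen's f with 160 visits is 0.264 for four groups and 0.223 for two.
- With 320 visits (both rounds) f for four groups is 0.186, but that is neither the stated sample size nor a difference between two means.

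**Figure 1 (printed 0.18).**
- 80 v 80: SE = sqrt(2/80) = 0.158; MDE = 0.393 one-sided, 0.443 two-sided.
- 120 v 40 (any stigma script against the reference): SE = sqrt(1/120 + 1/40) = 0.183; MDE = 0.454 one-sided, 0.511 two-sided.

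**Figure 2 (printed 0.17).** 40 v 40: SE = sqrt(2/40) = 0.224; MDE = 0.626 two-sided.

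**Figure 3 (printed 0.17), read as the overall index.**
- Design effect = 1 + 7 × 0.07 = 1.49; SE = sqrt(4 × 1.49/160) = 0.193; MDE = 2.486 × 0.193 = 0.480. With noncentral t on 18 df it is 0.499.
- With ICC 0 it is still 0.393.
- With unlimited visits in 20 clinics it is still 2.486 × sqrt(2 × 0.07/10) = 0.294.

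| Figure | Stated | Unadjusted MDE | Ratio | Unadjusted power at stated value | R-squared needed |
|---|---|---|---|---|---|
| 1 | 0.18 | 0.39–0.51 | 2.2–2.8 | 31%–17% | 0.79–0.88 |
| 2 | 0.17 | 0.63 | 3.7 | 12% | 0.93 |
| 3 | 0.17 | 0.48 | 2.8 | 22% (21% with t on 18 df) | 0.87 |

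The last column is 1 − (stated/MDE)², assuming that covariates reduce all variance components proportionally.

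**Can adjustment close the gap?**
- *Blocking.* Section 17.2 says that the 0.18 calculation does not use it. Crediting it at ICC 0.07 (stated only for figure 3) multiplies by sqrt(0.93) = 0.964, giving 0.38–0.49 for figure 1 and 0.60 for figure 2.
- *All between-clinic variance removed, figure 3.* 2.486 × sqrt(4 × 0.93/160) = 0.379. Reaching 0.17 needs residual variance (0.17/2.486)² × 40 = 0.187, a total R-squared of about 0.81.
- *Illustrative R-squared of 0.5 (assumed).* 0.28 (figure 1, 80 v 80 one-sided), 0.44 (figure 2) and 0.34 (figure 3).

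**Figure 3 read as a stigma difference.** With script main effects and about 20 visits per arm-by-script cell, SE = sqrt(4/20) = 0.447. The MDE is 1.11 one-sided and 1.25 two-sided (1.07 and 1.21 if the ICC 0.07 clinic effect cancels). The section 17.3 equation as printed has no script main effects; its contrast is then 20 v 20 within the trained arm, SE = sqrt(2/20) = 0.316, MDE 0.89 two-sided. No reading gives 0.17.

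**Size needed, unadjusted.**
- 0.18 at a 1:1 split: 4 × (2.486/0.18)², or 764 visits one-sided; 4 × (2.802/0.18)², or 970 visits two-sided.
- 0.17 pairwise: 2 × (2.802/0.17)², or 544 visits per script.
- 0.17 for the intervention: (2 × 1.49/8) × (2.486/0.17)² = 79.7, or 80 clinics per arm (1,280 visits), against 10 per arm planned.

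**The case against.** The strongest reply is that no planned model is unadjusted. Section 17.3 uses facility and SP fixed effects for stigma, and a doctor-level baseline mean with SP and script effects for the intervention, so the true detectable effects should be smaller than those above. That stands as a reason not to treat the unadjusted values as the planned precision. It does not rescue the printed ones: section 17.2 gives no R-squared or baseline correlation, and the shares needed are very high.

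Figure 1 is also under-specified, so no single replacement is its correct value. If it means one script against the reference, as beta1 and beta2 in section 17.3 do, the contrast is 40 v 40 and the MDE is 0.56 one-sided or 0.63 two-sided. The range of 0.39 to 0.51 covers contrasts that use all 160 visits, and this reading widens the gap.

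Finally, this is a pilot, figure 3 is secondary and cautiously worded, and the plan does not say that a later trial would be sized from these figures. This tempers the consequence for figure 3. It does not apply to figures 1 and 2, which serve the stated primary objective, or to the internal conflict between them, which needs no variance assumption.

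**Conclusion.** The concern holds. Figure 3 is the clearest case, because its inputs are almost complete: they give 0.48 to 0.50 SD, not 0.17. Figure 2 gives 0.63 SD if the scripts are equally split. Figure 1 gives at least 0.39 SD under any two-group contrast considered. At the stated effects, the unadjusted chance of missing a real difference is about 69–83%, 88% and 78%, where the plan implies 20%. These values assume SD 1 throughout, about 40 visits per script and no covariate gain. Only a variance reduction of roughly 80% or more, which the plan does not state, would bring the printed figures within reach. The section must be corrected.

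**What to change.** Restate section 17.2 as follows.

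- For each figure, give the contrast, the sidedness, and any assumed R-squared or ICC.
- Preferably estimate residual variance and ICC from the 160 baseline visits, which section 2.1 says have already been analysed descriptively, and recompute under the section 17.3 models.
- Otherwise print unadjusted values, labelled as such: 0.63 SD two-sided for beta1, beta2 and any script pair; 0.89 SD two-sided for beta3 (SE = sqrt(4/40) = 0.316); 0.48–0.50 SD one-sided for the overall intervention effect.
- State whether figure 3 concerns the overall index or the stigma difference. If a figure is given for the training effect on a script difference, label it about 1.25 SD two-sided, unadjusted, for a model with script main effects (1.21 if clinic effects cancel), and say whether the section 17.3 equation is meant to include those main effects.
- Remove the claim of power for small effects.

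The cost is less favourable stated figures, plus a short variance estimate from existing data if adjusted values are wanted. Sample size, visits and estimator stay as they are.

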### 3.0 Study Endpoints/Events/Outcomes

#### 3.1 Primary Endpoint/Event/Outcome

Our primary endpoint of the RCT phase of the study will be the quality of healthcare received by SPs in each clinical encounter with an enrolled provider. As a measure of the quality of healthcare provided in each interaction between physicians and standardized patients, we will create an index using 38 items from the structured post-interaction survey questionnaire administered to SPs following each unannounced visit. Individual items will be combined into a global index,  $\bar{s}_i$ , which is calculated as a weighted average of all 38 items, for which weights are calculated as the sum of its row entries in the inverted covariance matrix as follows:

$$\bar{s}_i = (1' \hat{\Sigma}^{-1} 1)^{-1} (1' \hat{\Sigma}^{-1} y_i)$$

where 1 is a column vector of 1s,  $\hat{\Sigma}^{-1}$  is the inverted covariance matrix, and  $y_i$  is a column vector of all items for individual  $i$ .

Using the analysis approach presented in section 17.3, we will estimate the impact of the intervention on the extent to stigma faced by SPs when presenting as MSM or HIV infected patients relative to the "standard" care experienced by the referent case scenarios of a straight, HIV uninfected man.

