#### 17.3 Statistical Analysis:

**Stigma Quantification:** Each of the four SP scenarios will be coded across two binary variables ("MSM" and "HIV") that will separately account for whether same-sex behaviors, HIV+ status, or both were announced by the SP during the provider visit. The scenarios will then be regressed on the quality of care index to assess the excess erosion of care observed in visits where SPs present as both HIV infected and as MSM, beyond the simple sum or product of the erosion experienced with only one of the attributes. Specifically, we will estimate:

$$\theta_{ijs} = \alpha + \beta_1 HIV_{ij} + \beta_2 MSM_{ij} + \beta_3 (HIV_{ij} * MSM_{ij}) + \gamma_j + \eta_s + \varepsilon_{ijs}$$

where  $\theta_{ijs}$  is the quality of care index as measured in SP interaction  $i$  in facility  $j$  conducted by SPs;  $HIV_{ij}$  is an indicator for the HIV status of the SP scenario in that given provider encounter;  $MSM_{ij}$  an indicator for the MSM status of the SP scenario in that given provider encounter;  $\gamma_j$  is a vector of facility fixed effects; and  $\eta_s$  is a vector of fixed effects for SPs. Here,  $\beta_1$  and  $\beta_2$  provides an estimate of HIV and

PROTOCOL TITLE: Standardized Patients to Address Intersectional Stigma  
 VERSION DATE: 07/23/2019

MSM stigma respectively, and  $\beta_3$  the estimate of stigma due to the presence of both HIV and MSM status.

Preliminary intervention effects: We will estimate the main intention-to-treat (ITT) impact of the training intervention using the Ordinary Least Squares (OLS) regression:

$$\theta_{idc} = \beta_0 + \beta_1 T_c + \beta_2 \bar{\theta}_{dc(t-1)} + \gamma X_{ic} + \varepsilon_{idc}$$

where  $\theta_{ict}$  is the healthcare quality index from SP interaction  $i$  with doctor  $d$  in clinic  $c$  measured at follow-up,  $T_c$  is a dummy variable that takes the value of 1 if the clinic was randomized to be offered training and 0 if in the control group. The coefficient of interest is  $\beta_1$ , which captures the ITT effect of training on the quality of care. We control for the average quality index from all SP interaction with doctor  $d$  at baseline,  $\bar{\theta}_{dc(t-1)}$ , as well as a vector of SP and disease script type (varying HIV and MSM status) fixed effects.  $\varepsilon_{idc}$  represents the idiosyncratic error, which we cluster at the clinic, the level of randomization.

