The ITT impacts reflect the effect of physicians being *offered* an opportunity to participate in training, not the causal effect of training itself. We therefore also estimate the effect of participating in training using the model

$$\theta_{idc} = \pi_0 + \pi_1 A_{dc} + \pi_2 \bar{\theta}_{dc(t-1)} + \varphi X_{ic} + \nu_{idc}$$

where  $A_{dc}$  is a measure of whether or not doctor  $d$  in clinic  $c$  attends the training and other variables are defined as above. We fit this equation by two-stage least squares (2sls) using the following first-stage equation:

$$A_{dc} = \delta_0 + \delta_1 T_c + \delta_2 \bar{\theta}_{dc(t-1)} + \zeta X_{ic} + \mu_{idc}$$

where the excluded instrument is the treatment assignment of doctor  $d$ 's clinic,  $T_c$ . We interpret the coefficient  $\pi_1$  as the local average treatment effect, or LATE, of participating in training on the quality of care provided.

While the analysis outlined above provides estimates of the effect of the training (or offer of training) on the quality of care provided to SPs presenting with cases of presumptive syphilis, the goal is to estimate the effect of the training on *enacted stigma*. That is, rather than the overall effect on the level of healthcare quality, we are primarily concerned with observing how the training affects the difference in the quality of care received by patients presenting as MSM or HIV-positive vs. those not, all else equal. Our two levels of randomization (SP-doctor interactions disease script types and clinics to treatment or control) allow us to estimate the causal effect of training offer (or participation) by estimating regressions analogous to the above, but interacting the dummy clinic treatment allocation with dummy variables for each SP script type. For ITT effects, we estimate

$$\theta_{idc} = \alpha_0 + \alpha_1 T_c + \alpha_{11} T_c \times V^{HIV+,MSM-} + \alpha_{12} T_c \times V^{HIV-,MSM+} + \alpha_{13} T_c \times V^{HIV+,MSM+} + \alpha_2 \bar{\theta}_{dc(t-1)} + \gamma \Gamma_{ic} + \varepsilon_{idc}$$

Where  $V$  are dummy variables for three of the four script variations (leaving out the HIV-, MSM- variation).  $\Gamma_{ic}$  is a vector of SP fixed effects. The coefficients  $\alpha_{11}$ – $\alpha_{13}$  represent the effect of training offer on the *difference* in healthcare quality provided

PROTOCOL TITLE: Standardized Patients to Address Intersectional Stigma  
VERSION DATE: 07/23/2019

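### Section 17.2 claims 80% power for a 0.17 SD reduction in EOC scores, but from its own inputs power is about 22% for the overall arm difference and about 11% for each arm-by-script (stigma) contrast

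*Combined protocol and SAP*

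**What the plan says.** The intervention paragraph of section 17.2 sets its goal as the effect on the quality of care index. It assumes 20 clinics allocated 1:1, "with an alpha level of 0.05 for a one-sided test", "an intra-cluster coefficient of 0.07", a "standardized quality of care index (with mean of 0 and standard deviation of 1"), and "a sample size of 160 SP clinic visits (8 visits per clinic on average"). It concludes that this gives "80% power to detect a reduction in EOC scores due to the intervention as small as 0.17 standard deviations". The abbreviations list expands EOC as erosion of care. No EOC score, scale or SD is defined.

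Two intervention targets appear elsewhere:

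- **Overall index difference.** Section 17.1 describes the secondary goal as a comparison of the quality index between arms. Section 17.3 presents the overall arm model as the main ITT analysis, with β₁ as its coefficient of interest.
- **Change in the script gap.** Section 3.1 frames the intervention effect as stigma relative to the "care experienced by the referent case scenarios of a straight, HIV uninfected man". Later in 17.3, the plan sets aside the overall level of quality and says "we are primarily concerned with observing how the training affects the difference in the quality of care received by patients", comparing MSM or HIV-positive presentations with the rest. The coefficients α₁₁–α₁₃ are meant to estimate this.

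Section 17.2 gives no power or detectable effect for α₁₁–α₁₃.

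**The concern.** The power statement carries a stigma label on inputs for a different contrast. In the stigma-quantification part of 17.3, erosion is a gap between scripts: "the excess erosion of care observed in visits where SPs present as both HIV infected and as MSM". A reduction in erosion due to training is then a double difference (disclosed minus referent, trained minus control). The inputs in 17.2 contain no script term and no referent cell; they describe 80 trained against 80 control visits. The two contrasts have very different precision.

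This is the plan's only power figure for the intervention, so readers will use it to judge how informative either result is. Someone who takes 80% power at 0.17 SD at face value would give too much weight to a non-significant arm-by-script result. A later trial planned from this figure would also start from the wrong precision.

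**Working it through.** **Inputs.** From 17.2: one-sided α 0.05, ICC 0.07, SD 1, 20 clinics 1:1, 160 visits, 8 per clinic. From 12.1: the four scripts are balanced over clinics. I take this as exactly 2 visits per script per clinic, so 10 × 2 = 20 visits in each arm-by-script cell. I take the 160 visits as the follow-up round.

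**Step 1: reproduce the plan's figure (overall arm difference).**

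- Design effect = 1 + (8 − 1) × 0.07 = 1.49
- SE = √(4 × 1.49 / 160) = 0.193
- Detectable effect at 80% power = (1.645 + 0.842) × 0.193 = 0.48 SD; with t on 18 df, 0.50 SD
- Power at 0.17 SD = Φ(0.17/0.193 − 1.645) = 22%

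The 0.17 is not reproduced. Ignoring clustering gives SE 0.158, detectable effect 0.39 SD and 28% power at 0.17 SD. Covariates would have to remove 1 − (0.17/0.48)² ≈ 87% of the variance to bring 0.48 down to 0.17. The figure does come out if 160 is entered as the number of clinics with 8 visits each (1,280 visits): SE = √(4 × 1.49 / 1280) = 0.068 and 2.487 × 0.068 = 0.17. That this is what happened is my inference from the arithmetic; the documents do not say so.

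**Step 2: one disclosed script versus the referent, by arm (each of α₁₁–α₁₃ as intended).** The clinic effect cancels within clinic, leaving variance 1 − 0.07 = 0.93.

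- SE = √(0.93 × 4/20) = 0.431
- Detectable effect = 2.487 × 0.431 = 1.07 SD one-sided; (1.960 + 0.842) × 0.431 = 1.21 SD two-sided
- With t on 18 df: 1.12 SD one-sided, 1.28 SD two-sided
- Power at 0.17 SD = Φ(0.17/0.431 − 1.645) = 11%
- Variance relative to the overall contrast: 0.186 / 0.03725 = 5.0

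**Step 3: all three disclosed scripts pooled versus the referent, by arm.** This contrast is not in the 17.3 model; it is shown for comparison.

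- SE = √(0.93 × 2 × (1/60 + 1/20)) = 0.352
- Detectable effect = 0.88 SD one-sided (0.91 with 18 df); 0.99 SD two-sided
- Power at 0.17 SD = 12%

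| Contrast | SE | 80% power at (one-sided; 18 df) | Power at 0.17 SD | Power at 0.48 SD |
|---|---|---|---|---|
| Overall (β₁) | 0.193 | 0.48; 0.50 | 22% | 80% |
| Pooled disclosed vs referent | 0.352 | 0.88; 0.91 | 12% | 39% |
| One script vs referent | 0.431 | 1.07; 1.12 | 11% | 30% |

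**Step 4: checks.** A 20,000-run simulation with clinic-level differences and t on 18 df gave, for one script versus the referent, an empirical SE of 0.43, 10.8% power at 0.17 SD and 77% at 1.07 SD. It gave 21.6% power at 0.17 SD for the overall difference. If covariates removed 25–50% of the within-clinic variance, the single-script detectable effect would still be 0.93–0.76 SD one-sided.

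**Step 5: the printed interaction equation.** The equation in 17.3 has arm, arm-by-script terms, the baseline index and SP fixed effects, but no script main effects. As printed, all control-arm scripts share one mean, so α₁₁–α₁₃ contrast scripts within the trained arm and are not double differences. Step 2 assumes the main effects are added.

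**The case against.** The strongest reply is that the sizing matches the target named in 17.1, in the opening of the 17.2 paragraph and in the overall model of 17.3, where β₁ is the coefficient of interest. EOC scores may be a loose label for the quality index, since the same sentence gives that index with mean 0 and SD 1. This stands. It makes the label a wording fault and the missing power for α₁₁–α₁₃ an omission, but it does not rescue the figure: 0.17 SD also fails for the overall difference.

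A reader might infer that the script gap is the only intervention goal, so the whole fall from 80% to about 11% comes from sizing the wrong contrast. The documents do not support that. They name both targets. At 0.17 SD, the fall from 80% to 22% arises because 0.17 does not follow from its own inputs; the change of contrast accounts for the further step from 22% to about 11%.

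A reader might also infer that a null interaction will be reported as proof of no effect, or that the next trial will be sized on the overall contrast. Neither is stated. Sections 5.1 and 17.2 call this a pilot, with the intervention effect a secondary goal for which adequate power is only plausible, and 15.1 anticipates a fully powered trial afterwards. This limits the severity.

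**Conclusion.** The point holds: the 80% power claim at 0.17 SD is valid for neither intervention target, and the contrast that 17.3 calls its main concern has no power statement. From the plan's inputs the design detects about 0.48–0.50 SD overall. For each arm-by-script contrast it detects about 1.1 SD one-sided or 1.2–1.3 SD two-sided.

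The single-script figures rest on 160 follow-up visits, exactly two per script per clinic, equal residual variance, no script-by-clinic variance (any would lower power), no covariate gain (any would raise it), and script main effects in the model. Two-sided values matter because 17.2 itself calls for two-sided tests when comparing scripts for stigma quantification.

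Severity: should be fixed. No estimate depends on the power sentence, and the goal is secondary in a pilot.

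**What to change.** In 17.2:

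- Replace 0.17 SD with about 0.48–0.50 SD, tie it to β₁ (overall quality index), and drop the EOC label.
- Give the detectable effect for α₁₁–α₁₃ as about 1.1 SD one-sided (1.2–1.3 SD two-sided), with the assumptions listed above.
- State that the pilot estimates the stigma effect with a confidence interval and is not powered to exclude moderate effects.

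In 17.3:

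- Add script main effects to the interaction equation.
- If a pooled disclosed-versus-referent figure is quoted (about 0.88–0.91 SD one-sided), add that contrast to the analysis.

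Across 3.1, 17.1, 17.2 and 17.3, state which intervention contrast is the main one.

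The cost is an edit to the protocol and SAP text and one corrected equation. No extra visits are needed. The stated detectable effect becomes less favourable.
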